Study Phases Enrollment Study Treatment Follow-Up	
 
Participants meeting inclusion/exclusion criteria at UNC
 
Meadowmont will be invited to participate. Those who consent will be fitted with the collar. Then, the at home treatment phase will begin where they report on collar efficacy. Finally, a follow up visit will be conducted to complete exit surveys.
 
	
Efficacy Evaluations	Significant improvement in tinnitus symptoms while wearing collar.	
Safety Evaluations	At intiial visit, team clinician will supervise collar fitting and evaluate for significant pain, discomfort, or adverse effect which will halt participation for that participant and be recorded. During at home study phase, participants will report any adverse effects with their daily recording of symptomatic efficacy.	
Statistical And Analytic Plan	One sided t test on tinnitus intensity while wearing collar vs. while not wearing collar will evaluate primary endpoint of collar relief efficacy. ANOVA analysis of intensity differences will elucidate effect of time, if any. One sided t test will evaluate secondary endpoints of quality of life	
DATA AND SAFETY MONITORING PLAN	Faculty mentor [name] is monitoring all safety related aspects. These include the evaluation of the initial collar fit, collar use education, and reporting of adverse events during at home period.	

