# 2.2 Secondary Objectives (or Aim)

The secondary objectives are to:

- Determine if the collar effect varies with time
- Evaluate changes in quality of life as a result of collar use
- Compare home use with in clinic use

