# 5.2 Efficacy Evaluations

#### 5.2.1 Diagnostic Tests, Scales, Measures, etc.

- Primary endpoint: symptom relief
  - Tinnitus aural intensity scale before and after collar administration at each visit and once daily for with collar and without collar intensity
- Secondary endpoint: QOL Impact
  - Tinnitus Handicap Index (Once at beginning of study, once at end)
  - Patient Reported Outcome Measurement Information System (PROMIS) scales in depression, anxiety, physical function, and satisfaction
- Secondary endpoint: Temporality
  - Aural intensity scale submissions will be plotted and compared over time course of study
- Secondary endpoint: Homes vs. clinic use
  - Supervised tinnitus intensity scale measurements will be compared to at home measurements to evaluate if perception of symptomatic intensity varies with environment

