#### 6.2 Secondary Endpoints

Secondary endpoints will include the following:

- The change in participant quality of life
- The effect of time on symptomatic relief
- The effect of medical supervision on symptomatic relief
- Adverse events (none are expected; however, the unlikely occurrence will be tabulated or a lack thereof shall be reported)

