#### 6.3.2 Efficacy Analysis

The primary analysis will be based on an intention to treat approach and will include all subjects who complete the study.

The primary efficacy endpoint will be the change in tinnitus intensity with and without the collar, averaged within and across each patient's completion of the tinnitus scales. This means that there will be 16 paired collar and no collar measurements per patient, one at each clinic visit and one each day during the 14 day intervening period. The significance of this change will be evaluated using a unidirectional t-test.

Secondary endpoints will include the following:

- Temporality of symptom relief
  - Subjects with and without collar scores will be averaged for each day of the study, ANOVA testing will evaluate for the presence of a significant time component.
- Supervised vs. unsupervised use
  - The mean relief recorded at the first and second visit will be averaged and compared avross patients with the mean relief recorded during at home use using a bidirectional t test.
- QOL impacts
  - Evaluated for each scale using bidirectional t test

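### As worded, the time analysis in section 6.3.2 does not make relief (the no-collar minus collar difference) the ANOVA response, so it conflicts with the Synopsis and does not answer objective 2.2

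*Combined protocol and SAP*

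**What the plan says.** The time question appears in five places.

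- Section 2.2 (secondary objectives): "Determine if the collar effect varies with time".
- Section 6.2 (secondary endpoints): "The effect of time on symptomatic relief".
- Protocol Synopsis, Statistical And Analytic Plan: "ANOVA analysis of intensity differences will elucidate effect of time, if any".
- Section 5.2.1 (temporality measure): "Aural intensity scale submissions will be plotted and compared over time course of study".
- Section 6.3.2, under the label "Temporality of symptom relief": "Subjects with and without collar scores will be averaged for each day of the study", after which ANOVA is to look for a significant time component.

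The first two set relief, or the collar effect, as the target. The Synopsis names the difference as the variable analysed. Section 5.2.1 refers only to submitted intensity scores. Section 6.3.2, the only place that describes the steps of the analysis, refers to averaged scores and does not name the ANOVA response.

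**The concern.** Whether relief changes with time is a question about the gap between two scores. An analysis of the scores themselves, or of their average, answers a different question: whether tinnitus gets louder or quieter over the study.

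The distinction matters here because the study is an unblinded single cohort with no control group. Tinnitus may fall over two weeks for reasons unrelated to the collar. A test on averaged scores could then give a significant time component that is reported as a time effect of the collar. Conversely, relief could fade while the average of the two scores stays level, and that test would have little chance of showing it. Two analysts, one following 6.3.2 literally and one following the Synopsis, could reach opposite conclusions from the same data.

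**Working it through.** The documents give no power or effect size for the time test, so there is no figure to reproduce. The check has two parts.

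**1. What each reading of the 6.3.2 sentence can test**

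Section 6.3.2 gives 16 paired measurements per participant, and section 6.4 gives 20 participants.

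- *The two scores averaged together, per participant and day.* The response is (no-collar + collar)/2. The day effect is drift in level; relief is not in the response.
- *Scores averaged across participants, one value per day and condition.* There are 16 × 2 = 32 values and 31 total degrees of freedom: 15 for day, 1 for collar, and 15 left. Those 15 are the collar-by-day term, which is the effect of interest. It serves as the error term and cannot be tested.
- *The difference averaged across participants, one value per day.* There are 16 values, and day uses all 15 degrees of freedom. Nothing is left for error.
- *The difference kept per participant and day.* Day is tested with 15 and 15 × 19 = 285 degrees of freedom. This answers objective 2.2, but 6.3.2 does not say it.

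**2. Illustration of the first reading against the last**

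From the documents: 20 participants, 16 days, mean intensity 5, average relief 1 point, alpha 0.05 (section 6.4 sets alpha for the principal endpoint only).

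Assumed: between-person SD 1.6, SD of individual relief 1.0, within-person SD 1.2 per score, independent errors, linear change over the study. The SD of a single score is √(1.6² + 0.5² + 1.2²) = √4.25 ≈ 2.1, close to the 2 in section 6.4.

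Error variances for the day effect:

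- average of the two scores: 1.2²/2 = 0.72
- difference: 2 × 1.2² = 2.88

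For a linear change of size δ across 16 equally spaced days, the squared centred day positions sum to 1.511. The noncentrality is λ = 20 × 1.511 × δ² / error variance.

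- (a) Both scores fall 1 point, relief constant. Average: λ = 30.22/0.72 = 42.0. Difference: λ = 0.
- (b) Relief changes 1 point, average level constant. Average: λ = 0. Difference: λ = 30.22/2.88 = 10.5.
- (c) Relief changes 1.5 points, average level constant. Average: λ = 0. Difference: λ = 30.22 × 2.25/2.88 = 23.6.
- (d) Collar score rises 1 point, no-collar score flat. The average moves 0.5: λ = 30.22 × 0.25/0.72 = 10.5. The difference moves 1: λ = 10.5.

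Rejection rates from 4,000 simulated trials per scenario:

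| Scenario | Average of the two scores | Difference |
|---|---|---|
| (a) common drift | 99.5% | 4.8% |
| (b) relief changes 1 point | 5.6% | 46% |
| (c) relief changes 1.5 points | 4.8% | 88% |
| (d) only the collar score moves | 45% | 47% |

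The noncentral F distribution with 15 and 285 degrees of freedom agrees: 99.5% for the average in (a); 46% and 88% for the difference in (b) and (c); 46% for both tests in (d).

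For sensitivity, a separate simulation used the 14 home days only and a day-to-day SD from 0.8 to 1.6. The averaged-score test rejected in 86% to 100% of trials under (a). Under a 1-point change in relief with constant level, the difference-based ANOVA rejected in 24% to 86%, and the averaged-score test in 4% to 5%. The sizes depend on the assumed split; the direction does not.

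**The case against.** The strongest reply is that the plan already contains the right answer. The Synopsis names intensity differences, the label above the disputed sentence refers to symptom relief, and sections 2.2 and 6.2 both target the collar effect or relief. Averaging for each day may mean only averaging over participants, before or after taking differences. Nothing in the documents ranks section 6.3.2 above the Synopsis. A reader might infer that the investigators have settled on the wrong test; the documents do not support that, because 6.3.2 never states the ANOVA response.

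This part of the reply stands, but it does not make the sentence adequate. Elsewhere the same section words a difference plainly: the primary endpoint reads "The primary efficacy endpoint will be the change in tinnitus intensity with and without the collar, averaged within and across each patient's completion", and the supervised-versus-unsupervised comparison is explicitly on mean relief. Only the time bullet speaks of scores. Even the sympathetic reading, one averaged difference per day, leaves no error term.

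A second reply concerns size. A reader might infer that fading relief would be missed completely. That holds only when the two scores move in opposite directions and cancel, as in (b) and (c). In (d), arguably a more natural form of fading, the averaged-score test has about the same power as the difference test (45% against 47%). What it cannot do is attribute the change to the collar, since a common drift gives the same kind of result. The daily plots in section 5.2.1 could also make opposite movements visible, though they are not a test. And if the two daily series were analysed separately, nothing would cancel, but neither analysis would have relief as its response.

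**Conclusion.** The point holds as a defect of wording and an inconsistency. Followed literally, the 6.3.2 sentence does not test whether the collar effect varies with time, and it conflicts with the Synopsis, which names the difference. It does not hold as a claim that a wrong test has definitely been chosen, or that every loss of relief would go unseen.

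The contrast of about 99% against 5% under common drift applies only if the two scores are averaged together. It rests on an assumed variance split and independent errors, so it illustrates the direction and is not an estimate for this trial. That the collar-by-day term is untestable when scores are averaged across participants to one value per day and condition follows from counting degrees of freedom and needs no variance assumption.

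The importance is minor to moderate: one secondary endpoint in a 20-person pilot. The primary analysis is unaffected, and the paired daily scores needed for the right analysis are already collected.

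**What to change.** Reword the temporality bullet in 6.3.2 to match the Synopsis. The response is each participant's daily no-collar minus collar difference. Day enters as a within-participant factor in a repeated-measures ANOVA or a mixed model that keeps the participant as a unit, so that daily values are not collapsed across participants before testing. Fitting both scores and testing the collar-by-day interaction in such a model is an equivalent way to put the question. Keep the daily averages of the two scores, but only for the descriptive plot in section 5.2.1.

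The cost is about one sentence of analysis wording, settled before the data are examined. No new data, visits or participants are needed.

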# 4.1.2 Between Visit (at home) phase

Patient wears collar for <4 hours total while awake for symptomatic relief as needed

Patient reports daily average tinnitus intensity with and without collar, length of use, and any adverse events through REDCAP email/text link

Continues daily for 14 days

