#### 9.4.2 Risk Assessment

#### Not Greater than Minimal:

- Psychological
  - Wearing the collar might be embarrassing for some patients. This is averted through a flexible at home protocol in which they are only asked to wear the collar on an as needed basis for symptomatic relief and report their efficacy. Patients will be allowed to withdraw from the study at any time.
- Confidentiality
  - Any study has potential consequences a breach of confidentiality, this study will avoid those consequences through maintenance of the data in a password protected REDCAP database accessible only to the research team, all of whom are HIPAA certified.
- Discomfort
  - The device is FDA approved for contact sports, and there are no adverse risks for the indicated population. However there is a possibility that patients will feel discomfort when wearing it. Care will be made to ensure the fitting is optimize the patient's needs. Possibility of mild discomfort if collar used incorrectly; this will be averted by counseling patients to not use the collar while sleeping and by fitting the collar correctly to the neck circumference of the subject at the initial visit.

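### With as-needed home wear and no rule for non-wear days, the daily means of relief can come from a changing group and drift although no participant's relief changes

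*Combined protocol and SAP*

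**What the plan says.** - **Objective.** Section 2.2 lists, among the secondary objectives, "Determine if the collar effect varies with time". Section 5.2.1 adds a plot of the intensity scores over the course of the study.
- **Time analysis.** Under section 6.3.2, scores on and off the collar "will be averaged for each day of the study", and ANOVA then tests for a time component. No subject term, fixed set of participants or rule for an incomplete day is given. The statistical row of the Protocol Synopsis describes the same analysis as an ANOVA of intensity differences.
- **Wear at home.** Section 4.1.2: "Patient wears collar for <4 hours total while awake for symptomatic relief as needed". Section 9.4.2 says of participants that "they are only asked to wear the collar on an as needed basis for symptomatic relief". No minimum wear is set.
- **Daily data.** Section 4.1.2: "Patient reports daily average tinnitus intensity with and without collar, length of use". Length of use does not enter the time analysis.
- **Pairs expected.** Section 6.3.2: "there will be 16 paired collar and no collar measurements per patient", one per visit and one per home day. Section 6.4 multiplies this to 320 for 20 participants.

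**The concern.** As-needed wear and a complete pair every day do not fit together. A day without wear gives no genuine with-collar rating, and the plan does not say what is then recorded. If the with-collar score is missing, a home day's mean relief is an average over those who chose to wear the collar that day.

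That choice is likely to depend on benefit. A participant who gets no relief can stop wearing the collar, keep filling in the diary and attend the second visit. That person is still a completer under section 6.3.2 but drops out of the later with-collar averages. The mean then rises because of who is in it.

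At stake is a named secondary objective. The abstract also lists sustained relief with home use among the main outcomes, and section 2 says the pilot data, if favourable, will support a multicenter grant application. A shift in who wears the collar could be read as sustained or growing relief.

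**Working it through.** **1. The plan's own count.** 14 home days + 2 visits = 16 pairs; 16 x 20 = 320. This reproduces the plan's figures. The home share is 14 x 20 = 280 pairs, which requires every participant to wear the collar on all 14 home days.

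**2. Expected drift with constant individual relief.** The documents give no wear pattern, so these inputs are assumed: r = share who benefit, R = their constant relief in points, h = daily chance that someone without benefit stops wearing the collar, d = home day. Benefiters keep wearing it. Expected mean relief among wearers on home day d is

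M(d) = rR / [r + (1 - r)(1 - h)^(d - 1)].

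With r = 0.5 and R = 2, M(1) = 1 / (0.5 + 0.5) = 1.00. On day 14:

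| h per day | (1 - h)^13 | M(14) | Rise | Home pairs left of 280 |
|---|---|---|---|---|
| 5% | 0.513 | 1 / (0.5 + 0.5 x 0.513) = 1.32 | 0.32 | 242 |
| 10% | 0.254 | 1 / (0.5 + 0.5 x 0.254) = 1.59 | 0.59 | 217 |
| 20% | 0.055 | 1 / (0.5 + 0.5 x 0.055) = 1.90 | 0.90 | 188 |

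Over r = 0.25 to 0.75, R = 1 to 2 and h = 5% to 20%, the rise runs from 0.10 (r = 0.75, R = 1, h = 5%) to 1.22 points (r = 0.25, R = 2, h = 20%), with 261 down to 142 pairs left. For scale, section 6.4 takes 1 point as its minimum effect for the primary endpoint.

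**3. Simulation.** 2,000 runs, 20 participants, 14 home days, r = 0.5, R = 2, between-subject SD 0.5 within each group, day-to-day SD 1 (all assumed), and no change in anyone's relief. At h = 5%, 10% and 20%:

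- The day means rose on average by 0.35, 0.62 and 0.89 points.
- A linear day effect fitted with subject effects gave a mean change of about 0.00. Its false-positive rate was 4.8% to 5.6%, including the case of no stopping.

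**4. Does the test flag the drift?** This depends on which ANOVA is meant.

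- Linear trend on the 14 day means: significant in 32%, 64% and 85% of runs (5.2% with no stopping). With a larger day-to-day SD of 1.2 x sqrt(2) = 1.70, about 15% to 48%.
- One-way ANOVA of individual differences by day, ignoring subject: 0.2%, 2.6% and 16.7% (0.0% with no stopping). With the larger SD, about 1% to 12%.

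The one-way form is mostly quiet because differences between people inflate its error term. It is insensitive to real change for the same reason.

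**The case against.** The strongest reply is that the plan intends complete, paired data. It asks for both scores every day, counts 16 pairs per patient and, in the synopsis, analyses differences. The diary form is not in the document, so how a non-wear day is recorded is unknown. This stands as a limit: missing with-collar scores are an inference from as-needed wear, not a stated fact. It does not settle the matter, because the plan has no rule that would make the two statements agree.

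Four stronger readings are tempting, and the documents do not support them.

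- **The with- and without-collar means come from different people on the same day.** This holds only if the two scores are averaged separately. The synopsis wording on differences, and the word paired in section 6.3.2, point to same-person differences. Membership that changes from day to day remains a problem on either reading.
- **The planned test will produce false positives.** The high rates belong to a trend on day means. A one-way ANOVA exceeds 5% only towards the fastest stopping rates assumed here.
- **The bias favours the collar.** It does if non-benefiters stop. If people wear it only on bad days or stop once better, the direction may differ.
- **Withdrawals cause it.** Section 4.2.1 deletes withdrawn participants' records apart from adverse events. The drift comes from people who stay in the study but stop wearing the collar. Section 4.2 allows discontinuation for poor adherence, which might remove some of them, but that is discretionary.

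The second visit also dampens the effect, since every completer is scored with the collar again. In a scenario with about 70% of non-benefiters stopped by home day 14, adding both visits cut the apparent rise from about 0.54 to 0.42 points. That mixes time with supervision and does not correct the home-day curve.

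**Conclusion.** The point holds for the 14 home days. Where non-wear days yield no with-collar score, averaging across subjects by day lets the time curve move through changing membership alone. The rise is about 0.3 to 0.9 points in the central scenario and 0.10 to 1.22 over the wider range, with no individual change. These sizes rest on assumed benefit shares, stopping rates and SDs, and the direction is not fixed. The day means and the plot are affected whichever ANOVA is used; the significance test may or may not be. This concerns a secondary question in a 20-person pilot, but the correction is cheap and should be made.

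**What to change.** In section 6.3.2, and in the diary instructions where relevant:

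1. State that a day without collar wear is recorded as having no with-collar score.
2. In line with the synopsis, use each participant's own same-day difference, and test time with a repeated-measures or mixed model with subject effects instead of cross-subject day averages.
3. Analyse the 14 home days separately from the two clinic visits.
4. Show under each day of the section 5.2.1 plot how many participants contribute a pair.
5. Reconcile the 16-pair count in section 6.3.2, and the use of 320 in section 6.4, with as-needed wear.

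An estimate in participants with pairs in both home weeks may be added as descriptive only, because it selects continued wearers. Subject effects remove the between-person drift shown above, but not bias from stopping that depends on relief nobody recorded. The daily counts and the length-of-use data help to judge that remainder.

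The cost is revised wording, a recording rule, a row of counts and minor analysis work. No new measurement is needed, and the interval may be slightly wider.

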#### Surveys and Scales:

The Tinnitus Handicap Inventory (THI) is a 25-item validated survey that evaluates the degree of impact a patient's tinnitus has on their quality of life. It is currently the first line survey for systemic impacts of tinnitus and is attached at the end of this proposal. In addition, NIH validated patient reported outcome measurement information system (PROMIS) questionnaires on anxiety, depression, physical function, and satisfaction will be administered before and after the treatment period to evaluate the collar's broader impact on patient quality of life (see end of proposal). Additionally, a custom tinnitus intensity scale modeled after the numerical pain scale with be used to assess relief. Lastly, a single item Likert scale inquiring about use of the collar when symptoms present will be applied to evaluate adherence.

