#### 6.4 Sample Size and Power

For the principal endpoint, the tinnitus intensity scale ranges from 1-10. Assuming an average tinnitus intensity of 5 and a standard deviation of plus or minus 2 (such that 95% of the venous pulsatile tinnitus population has tinnitus intensity between 1 and 9). Intensity scale measurements will be averaged across individual submissions and across participants. With 16 paired evaluations per participant and 20 participants total, that creates 320 non collar tinnitus intensity measures.

Setting an alpha of p=.05 and a power of 0.8 (beta=0.2), we expect a minimum effect of a 1 point decrease between the no collar and collar measurements. To be conservative, we will preserve the 2 point standard deviation assumed for the baseline measure to apply to the collar relief measure. These parameters allow us to evaluate the viability of our sample size.

$$n_{g} \doteq (z_{lpha/2} + z_{eta})^{2} rac{\sigma_{1}^{2} + \sigma_{2}^{2}}{(\mu_{1} - \mu_{2})^{2}}$$

Where n is the number of analyses that will allow our minimum effect size to be significant Substitution lends us the following

 $\begin{array}{l} n_{\rm g} = (1.96 {+}~ 0.8416)^{2*} (2^2 {+} 2^2) / (2)^2 \\ n_{\rm g} = 15.86 \end{array}$ 

Not only is our overall study well in exceeding the number of intensity measurement differences needed to measure a significant effect; we will be able to assess the significant effect within each participant, given that each participant will complete both the with and without collar scales a total of 16 times. This gives our study strong internal and external validity.

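### Quality of life is one secondary endpoint tested separately on five scales, with no key scale and no multiplicity control, and the plan contradicts itself on whether the tests are one-sided

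*Combined protocol and SAP*

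**What the plan says.** Section 6.2 gives quality of life as one item in its list of secondary endpoints: "The change in participant quality of life". Section 5.2.1 names the instruments. One is the "Tinnitus Handicap Index (Once at beginning of study, once at end"), called the Tinnitus Handicap Inventory in section 1.3. The others are the "Patient Reported Outcome Measurement Information System (PROMIS) scales in depression, anxiety, physical function, and satisfaction". Section 1.3 confirms the four domains and their timing: "questionnaires on anxiety, depression, physical function, and satisfaction will be administered before and after the treatment period". That makes five scales, each measured before and after the home period.

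The analysis of these scales in section 6.3.2 is one line: "Evaluated for each scale using bidirectional t test". The Protocol Synopsis (Statistical And Analytic Plan) says something different: "One sided t test will evaluate secondary endpoints of quality of life".

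The plan has no key scale, composite, testing order or adjusted significance level for quality of life, and it does not label these tests exploratory or descriptive. Section 1.3 says of the THI, "It is currently the first line survey for systemic impacts of tinnitus", but the analysis section gives it no priority. The only significance level is in section 6.4, where it is set for the principal endpoint: "Setting an alpha of p=.05 and a power of 0.8 (beta=0.2".

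**The concern.** A single endpoint invites a single conclusion. Five separate significance tests produce five p values, and the plan does not say how they become one statement about quality of life. An author who finds one significant scale out of five could report it as a quality-of-life effect without departing from anything written in the plan. The error rate of such a statement is that of the best of five tests, which is higher than that of one test.

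The disagreement on sidedness adds a second free choice. A result could be significant under the synopsis and not under section 6.3.2, and the reader could not tell which test had been planned.

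At stake is how much a reported quality-of-life finding can be trusted when it is published, or when it is used to choose outcomes for a later trial.

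**Working it through.** The plan states no family-wise error rate for quality of life, so there is no figure of its own to reproduce.

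**Inputs**
- Number of tests: 5 (THI plus four PROMIS domains; section 5.2.1).
- Test: two-sided, one per scale (section 6.3.2). The synopsis's one-sided version is worked as an alternative.
- Significance level per scale: .05. This is an assumption, taken from the only level in the document (section 6.4).
- Evaluable participants: 20 (section 3.2.2).
- Correlation between changes on the five scales: not given. A common correlation of 0, 0.5, 0.7 and 0.9 is assumed in turn.

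**Step 1. Independent scales, no true change on any**
- At least one false result in either direction: 1 − 0.95^5 = 1 − 0.7738 = 22.6%.
- At least one false benefit (each two-sided .05 test has .025 in the favourable tail): 1 − 0.975^5 = 1 − 0.8811 = 11.9%.
- For one scale alone the same two rates are 5% and 2.5%.

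**Step 2. Correlated scales**

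With common correlation ρ and critical value c = 1.96, the five test statistics share a normal factor u. The chance that none is significant is

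∫ φ(u) · [Φ((c − √ρ·u)/√(1−ρ)) − Φ((−c − √ρ·u)/√(1−ρ))]^5 du,

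and one minus this is the rate for either direction. Dropping the second Φ term gives the false-benefit rate. The one-sided .05 version also drops that term and uses c = 1.645. The last row uses .05/5 = .01 per two-sided test.

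| | ρ = 0 | 0.5 | 0.7 | 0.9 |
|---|---|---|---|---|
| Two-sided .05, any false result | 22.6% | 18.3% | 14.8% | 10.2% |
| Two-sided .05, false benefit only | 11.9% | 9.1% | 7.4% | 5.1% |
| One-sided .05 (synopsis), false benefit | 22.6% | 16.6% | 13.5% | 9.5% |
| Bonferroni, or Holm's first step, any false result | 4.9% | 4.2% | 3.5% | 2.3% |

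**Step 3. Check at the planned size**

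Simulated paired t tests with 20 participants (100,000 runs) gave 22.5%, 18.7% and 15.2% for any false result at ρ = 0, 0.5 and 0.7. For false benefit they gave 11.8%, 9.4% and 7.6%. The normal approximation is therefore adequate here.

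**Step 4. Sidedness**

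At ρ = 0.5 the chance of a false benefit is 9.1% under section 6.3.2 and 16.6% under the synopsis, a ratio of 16.6/9.1 = 1.8. The contradiction therefore changes the result materially.

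**The case against.** The strongest reply is that these are prespecified secondary scales in a 20-person pilot. The PROMIS scales measure different things, and reporting each domain at its own error rate is legitimate. Family-wise error matters only if the five results are pooled into one claim, and no sentence in the plan says that one significant scale is enough. That last point is correct. A reader might infer an any-one-scale success rule, but the plan merely leaves room for it.

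Three other stronger readings also go beyond the documents.
- **That the chance of falsely claiming a benefit is 15–23%.** That range is for a false result in either direction, including apparent worsening, at correlations from about 0.7 down to 0. Under the two-sided tests of section 6.3.2, false benefit alone is about 7–12% over the same range.
- **That quality of life is really a main outcome.** One sentence of the Abstract groups it with the main outcomes. The same Abstract calls it a secondary effect to be piloted, and the synopsis objectives and sections 2.2, 5.2.1, 6.2 and 6.3.2 all make it secondary.
- **That a quality-of-life claim would go into the multicentre grant application.** Section 2 ties that application to pilot data showing efficacy and does not mention quality of life.

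It is also fair to say that section 1.3 describes the THI's standing in the field and does not rank it within this study. Nor would naming it remove the larger limitation: an unblinded before-after comparison without controls can show change that the collar did not cause.

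What the reply does not answer is that the plan specifies significance tests for a single endpoint, does not call them exploratory, and gives no rule for combining them.

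**Conclusion.** The point holds as a gap in the plan, at low priority. One secondary endpoint is tested five times with no key scale and no adjustment, so a quality-of-life statement resting on the best of five scales has a false-positive rate of about 10–23% in either direction. For false benefit alone the rate is about 5–12%, or roughly two to five times the 2.5% for one scale.

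These figures rest on .05 per scale, two-sided tests and assumed correlations between 0 and 0.9. The upper ends require independence; related questionnaires would probably fall lower in the range, but the documents give no figure for this.

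The conflict between the synopsis and section 6.3.2 on sidedness needs none of these assumptions and should be corrected in any case. The consequence is limited because quality of life is secondary in an uncontrolled pilot.

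**What to change.** Replace the quality-of-life line in section 6.3.2 with a statement along these lines: change in THI total score from the first to the second visit is the single quality-of-life test, by a paired t test at two-sided .05. The four PROMIS scales are reported as mean changes with 95% confidence intervals and labelled supportive. If p values are shown for them, they are Holm-adjusted.

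Change the synopsis in the same edit so that it no longer specifies a one-sided test for quality of life. Make both changes before the data are examined, because a key scale chosen afterwards gives no protection.

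The rate of a false quality-of-life result then becomes 5% in either direction and 2.5% for benefit. If the sponsor prefers not to rank the scales, Holm across all five (4.9% or less in the table above) or an explicit exploratory label on all five would also close the gap.

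The cost is a sentence in the analysis section and a correction to the synopsis, with no extra participants, visits or data. The downside is that a change seen on a PROMIS scale alone could no longer carry the quality-of-life claim.
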